3.3 Secondary Safety Endpoints

- 1) Symptomatic intracerebral hemorrhage within 18-36 hours.
 1. Defined as the SITS-MOST definition: Increase in NIHSS of ≥ 4 points and PH-2/rPH-2.²³
- 2) All-cause mortality.
- 3) Rates and types of peri-procedural or device-related complications.

3.4 Exploratory Analyses

- 1) Ordinal ITT and as-treated analysis of primary outcome comparing three groups (CS, GA IV, GA inhalational) adjusting for stratification variables.
- 2) Multivariable adjusted analysis (including stratification variables) for both primary (mRS 0-2) and ordinal analysis of 90-day mRS outcomes, to include (but not limited to) baseline variables known to be clinically associated with stroke outcomes:
 - a. Age
 - b. NIHSS
 - c. Time from stroke onset-to-EVT groin puncture
 - d. IV-tPA treatment before EVT
 - e. Atrial Fibrillation
- 3) Duration of time during EVT spent below a systolic blood pressure of 140mmHg.
- 4) Total ICU and ventilator days.
- 5) Subgroup analyses to test for heterogeneity in patient benefit and Provider Skill:
 - a. Proximal vs. Distal occlusion location (ICA+M1-MCA vs. others)
 - b. High-volume vs. low-volume centers
- 6) Costs from a health system perspective

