Design	Multicenter, randomized, comparative effectiveness trial with un-blinded caregivers but blinded assessors (PROBE – Prospective Randomized Outcome Blinded Endpoint).
Study Population Overview	260 total acute ischemic stroke patients with proximal intracranial arterial occlusions treated with endovascular therapy within 16 hours of symptom onset. Patients must not require intubation for any clinical indication. Arterial occlusion must be demonstrated by either CT-angiogram (CTA) or MR-angiogram (MRA).
Intervention	
Time of randomization is study time=0. Patients will be randomized 1:1 to receive during endovascular therapy either:
 
 1) General anesthesia (balanced for equal randomization into intravenous vs. inhalational) or 2) Sedation 
Both GA and CS delivered and managed by anesthesiologist.

Primary Outcome	Independent functional outcome as measured by the modified ordinal Rankin Scale (mRS) at 90 days assessed by study personnel blinded to treatment.
Secondary Outcomes	
 1) Dichotomized mRS at 90 days (0-2 vs 3-6) 2) Safety as measured by rates of symptomatic intracerebral hemorrhage within 24-36 hours after endovascular therapy. 3) Angiographic reperfusion defined as modified TICI score $\geq 2b$. 4) Peri-procedural complications. 5) Difference in 24-36-hour NIHSS scale. 6) Proportion of independent functional outcome at 90 days in GA patients treated with inhalational vs. intravenous medications. 7) Difference in quality of life at 90-days.

IRB NUMBER: HSC-MS-17-043

Study Duration	
Total trial duration: 24 ± 4 months
 
 
Enrollment – approximately 18 months with 6 months of data-monitoring and statistical analysis 
Patient participation - 90 days
Statistics	
 
Planned number of sites (US + international): 10-15. 
Sample size: 260 patients randomized 1:1 (130 per group). 
Final analysis uses a Bayesian approach to obtain odds ratio (OR) of good functional outcome at 90-days. Bayesian prior assumes treatment equipoise and uses a neutral, informative prior (OR=1.0; 95% credible intervals of 0.3-3.0). 
Trial success is defined as a >80% posterior probability that GA is superior (OR >1.0 of 90-day mRS) to CS.

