19	Post-Hoc Meta-Analysis of 9 studies	Sedation	
 • No difference in treatment times between the two groups 	GA associated with: 
 ↑mortality OR 2.6, ↑respiratory complications OR 2.1 ↓good clinical outcomes (OR = 0.43) 	
 - GA patients with higher NIHSS presenting scores. - n=1956
20	RCT Monocentric	GA - no support for CS advantage	
 • No significant difference (P=0.82) in primary outcome (24 hour NIHSS) between groups. • ↑ mRS ≤2 at 90d 37%-GA v. 18% CS without mortality diff. 	
 GA had more: 
 - hypothermia (32%, P<0.001) - delayed extubation (49.3%, P<0.001) - pneumonia (13.7%, P=0.03) 	Only RCT that randomized EVT patients to either GA or CS. Sedation – 77; GA - 73
Campbell (ISC 2017)	Post-Hoc Meta-Analysis 5 RCTs	Sedation	
 • Both CS & GA superior compared to usual care • Equivalent procedure complications 	
 ↑good outcomes in non-GA group (OR 1.6). ↑ pneumonia in GA group (16% v 9%), - Randomization to treatment time prolonged in GA 	HERMES collaboration; n=1287; NIHSS, age, onset to random. times comparable CS v. GA

A recent retrospective study of a multi-hospital administrative database between 2006-2013, found 80% of 2515 EVT patients received GA, whereas 20%, received CS.²¹ These findings suggest the majority of neuro-interventionists preferred GA. Since that time, multiple retrospective studies have been published (detailed in table 1) that suggest CS may be preferable to GA. We recently sent a questionnaire to vascular neurologists and both neurology and neurosurgery trained neuro-interventionalists. The aim was to determine the state of anesthesia equipoise among physicians who perform or direct care for EVT stroke patients. Notably, the questionnaire was sent 4 months after publication of the SIESTA trial. EVT specialists were asked if a randomized trial was still needed – Figure 1. Out of 97 respondents, the responses were similar.

[figure not shown]

Figure 1. Results of questionnaire from comprehensive stroke center's opinion for a current randomized trial of anesthesia in EVT.

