5.0 STUDY POPULATION

5.1 Inclusion Criteria

1. Acute ischemic stroke due to large intracranial vessel occlusion demonstrated on CT-angiography in the following anterior circulation locations that will be treated by endovascular therapy (EVT):
 - a. Internal Carotid Artery (terminal “T” or “L-type”- occlusion)
 - b. Middle Cerebral Artery (MCA) M1 or proximal M2
 - c. Anterior Cerebral Artery (ACA) A1 or proximal A2
 - Patients who receive IV-tPA thrombolysis are eligible provided the drug was delivered within 4.5 hours of stroke onset or last seen normal and in accordance with local hospital standard of care.
 - Patients who receive TNKase are also eligible, given that drug was delivered in accordance with the local hospital standard of care.
2. Ages 18-90.
3. National Institute of Health Stroke Scale (NIHSS) score 6-30
4. Time of stroke symptom onset of last seen normal to start of EVT (defined as groin puncture) \leq 16 hours.
5. Limited infarct core, as defined below and adapted from the 2018 American Heart Association guidelines²⁸
 - a. For patients presenting \leq 6 hours from time of symptom onset or last seen normal, Alberta Stroke Program Early Computed Tomography Score (ASPECTS) \geq 6
 - b. For patients presenting $>$ 6 hours and \leq 16 hours from time of symptom onset or last seen normal, they must satisfy EITHER ONE of the two following criteria:
 - i. Ischemic core by CT Perfusion or MRI/MR Perfusion $<$ 70 mL, a ratio of volume of penumbral tissue to infarct core of \geq 1.8, and absolute volume of penumbral tissue of \geq 15 mL²⁹

OR

- ii. For patients with NIHSS \geq 10, infarct core of $<$ 31 mL by CT Perfusion or MRI; For patients with NIHSS \geq 20, infarct core $<$ 51 mL.³⁰
6. Subject willing/able to return for protocol required follow up visits.
7. No significant pre-stroke disability (modified Rankin Score must be \leq 2).
8. Females of childbearing potential must have a negative serum or urine pregnancy test.
9. Patient or patient’s legally authorized representative has given Informed Consent according to Good Clinical Practices (GCP) and/or local IRB policies.

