6.2 Treatment Period

6.2.1 Endovascular Procedure and Time Metrics

As recommended by the AHA/ASA, the first line therapeutic embolectomy device should be a stent retriever. The use of a proximal balloon guide catheter or a large-bore distal-access catheter, rather than a cervical guide catheter alone, in conjunction with stent retrievers may be beneficial. Future studies should examine which systems provide the highest recanalization rates with the lowest risk for nontarget embolization

Additional EVT therapies including, but not limited to, intra- or extracranial angioplasty ± stenting; antithrombotics (oral, IV or IA antiplatelets or anticoagulants) intra-arterial thrombolytics; are left to the decision of the local treatment team. Conversely, in general, off-label use or therapies not supported by scientific evidence are discouraged. Importantly, the use of these therapies will not be considered a protocol deviation.

Time to reperfusion in EVT trials is correlated with improved outcomes and societies have published position statements on timing metrics. The current protocol provides guidance for centers derived from these recommendations (see table 3).²⁶

Table 3. SEGA recommended guidelines for timing metrics

Acute Stroke Time Metric	Maximal Target Time
Door to Imaging (parenchymal imaging – non-contrast CT, MRI)	15 minutes
Door to IV-tPA bolus/ TNKase	60 minutes
Door to Groin Puncture	90 minutes
Angiosuite arrival to Groin Puncture	20 minutes
Door to Reperfusion	150 minutes IRB NUMBER : HSC-MS-17-0436

The following intra-procedure (thrombectomy) variables will be collected (see CRFs for further details):

- Door to puncture time
- Decision of intervention to puncture time
- Time from puncture to first recanalization attempt
- Time to Revascularization: defined as arterial puncture to TICI $\geq 2b$ revascularization or end of procedure.
- Revascularization assessment at the end of the procedure (using Thrombolysis in Cerebral) Infarction (TICI) score.
- Number of recanalization attempts (i.e. thrombectomy attempts or stent-retriever passes)
- Name of the mechanical retrieval device used
- Utilization of aspiration technique
- Failure to reach clot

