7.4 Anesthesia Monitoring

Invasive hemodynamic monitoring should be attempted prior to induction of GA to allow for tight hemodynamic control. To limit any delay in time to revascularization, attempts to establish peripheral invasive arterial access should be limited to 5 minutes; after that time, continuously-cycled non-invasive blood pressure measurements should be performed until invasive hemodynamic monitoring can be achieved through the femoral sheath. SBP should be maintained at 140 to 180 mmHg throughout with phenylephrine and/or norepinephrine as needed. Patients who are converted from sedation who already have invasive hemodynamic monitoring through the femoral sheath do not need additional arterial access.

End-tidal CO₂ concentration (PETCO₂) in patients receiving GA should be maintained at 35 to 40 mmHg (corresponding to a PaCO₂ ~40-45 mmHg).

All patients who are deemed medically appropriate for extubation should be awakened and extubation attempted at the conclusion of the procedure. Muscle paralysis should be reversed at the conclusion of the procedure using neostigmine or sugammadex; those patients with deep neuromuscular blockade that precludes reversal with neostigmine should be reversed with an adequate dose of sugammadex to avoid unnecessary prolonged intubation.

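### Section 3.4(2) adjusts for onset-to-groin-puncture time as a baseline covariate, although puncture follows randomization and may itself be changed by the assigned anesthesia

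*Combined protocol and SAP*

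**What the plan says.** Section 3.4, item 2 plans multivariable models for mRS 0-2 and for the ordinal 90-day mRS. They include the stratification variables and an open-ended list described as "baseline variables known to be clinically associated with stroke outcomes". The list holds age, NIHSS, IV-tPA before EVT, atrial fibrillation and, as item 2c, "Time from stroke onset-to-EVT groin puncture".

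Other parts of the protocol fix the order of events:

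- Synopsis, Intervention: "Time of randomization is study time=0". Patients are randomized to the anesthesia they will receive during EVT.
- Section 5.1, criterion 4: the 16-hour window runs to the "start of EVT (defined as groin puncture".
- Section 6.2.1: "The following intra-procedure (thrombectomy) variables will be collected". Door-to-puncture time heads that list.
- Section 7.4: "Invasive hemodynamic monitoring should be attempted prior to induction of GA". Attempts at peripheral arterial access are limited to 5 minutes.

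The primary model in section 9.2 adjusts only for the stratification variables and does not use puncture time. Section 9.2 also provides for secondary analyses that control for important arm differences in outcome-related baseline variables.

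**The concern.** A covariate measured after randomization can respond to treatment. Care is un-blinded, so the work between randomization and puncture is done with the arm known, and in the GA arm it may include arterial access and induction. The protocol also holds that delay matters: section 6.1 links 20-minute reperfusion delays to worse outcomes. Puncture time may therefore lie on the path from assigned anesthesia to mRS.

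If it does, conditioning on it compares the arms at equal puncture time. The result is a direct effect. The primary objective in section 2.1 asks whether GA improves 90-day outcome compared with sedation, which includes any delay that GA brings. Nothing in the protocol says that item 2 is meant to estimate a direct effect.

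Two sets of results are exposed. The first is the exploratory adjusted ORs. The second is conditional: if puncture time keeps its baseline label, an arm difference caused by the anesthesia could be read under section 9.2 as chance imbalance and adjusted away there too.

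**Working it through.** **Is the covariate measured before or after randomization?** Time zero is randomization (synopsis). Enrollment is complete once the arm is assigned (section 4.2). The randomized anesthesia is given during EVT, and EVT starts at puncture (section 5.1). Puncture therefore follows randomization. This is inferred from several sections rather than stated in one sentence, but no section allows the reverse order. The other four listed covariates can all be fixed before randomization.

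**Can the arm change it?** The evidence in the documents is mixed.

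- For: section 7.4 adds a step before GA induction. Table 1 reports, from a pooled analysis of five RCTs whose patients were not randomized to anesthesia, "Randomization to treatment time prolonged in GA".
- Against: Table 1 also reports, from a meta-analysis of nine studies, "No difference in treatment times between the two groups".
- Either way: the background says that GA may delay recanalization and that movement under sedation may do so too.

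**Scale from the plan's own figures.** The plan gives no figure for this analysis. For the primary outcome, Appendix II states power 0.80 and type I error 0.18 at N=260, OR 1.53, 10% crossover and a 0.80 posterior threshold. A normal approximation reproduces both:

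- SE of the log OR from the proportional-odds information, N/12 × (1 − Σp̄³), where p̄ is the average of the two arms' mRS proportions: 0.218.
- Log OR after 10% crossover: 0.382.
- With the Normal(0, 0.57) prior, success needs an estimate above 0.842 × 0.218 × √(1 + 0.218²/0.57²) = 0.197.
- Power = 1 − Φ((0.197 − 0.382)/0.218) = 0.80. Type I error = 1 − Φ(0.197/0.218) = 0.18.

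**Size of the shift.** Let d be the mean delay of puncture under GA in minutes and k the OR for a better mRS per hour of delay. Then

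adjusted log OR = total log OR − ln(k) × d/60.

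Neither d nor k is in the documents, so both are assumed. The 5-minute value echoes the access limit in section 7.4. The 20-minute value echoes the angiosuite-to-puncture target in Table 3, which is a whole interval and not an arm difference. The values of k are pure assumption.

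| d (min) | k per hour | Shift in log OR | Share of ln 1.53 = 0.425 | Total OR 1.00 appears as | Total OR 1.53 appears as |
|---|---|---|---|---|---|
| 5 | 0.9 | 0.105 × 5/60 = 0.009 | 2% | 1.01 | 1.54 |
| 5 | 0.7 | 0.357 × 5/60 = 0.030 | 7% | 1.03 | 1.58 |
| 20 | 0.9 | 0.105 × 20/60 = 0.035 | 8% | 1.04 | 1.59 |
| 20 | 0.7 | 0.357 × 20/60 = 0.119 | 28% | 1.13 | 1.72 |

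Against the SE of 0.218, the shift runs from 0.009/0.218 = 0.04 to 0.119/0.218 = 0.55 standard errors. If sedation caused the same delays, a total OR of 1.00 would appear as about 0.99 to 0.89.

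**Check by simulation.** Proportional-odds data were generated with 200,000 patients per case, the Appendix II sedation rates, a total OR of 1.53 and an assumed mean of about 5 hours from onset to randomization. The two adjustments gave:

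| d (min) | k per hour | OR adjusted for puncture time | OR adjusted for onset-to-randomization time |
|---|---|---|---|
| 5 | 0.9 | 1.53 | 1.52 |
| 10 | 0.9 | 1.57 | 1.54 |
| 10 | 0.8 | 1.58 | 1.52 |
| 20 | 0.8 | 1.65 | 1.53 |

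The pre-randomization covariate returns the total effect to within simulation error, and the puncture-adjusted OR is higher in every case.

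**The case against.** The strongest reply is that little depends on this. Item 2c sits in an exploratory model, and the total effect is estimated and reported by the primary analysis and the dichotomized mRS analysis, neither of which uses puncture time. That stands, and it limits the consequence.

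The evidence that anesthesia changes puncture time in particular is also thin. The background and section 6.1 speak of recanalization or reperfusion. The sedation remark concerns movement on the table, which is largely an event after puncture, so the reverse scenario has weak support. Section 7.4 does not say that the arterial line or induction must come before puncture, and it caps the attempts in order to limit delay. This stands too: the bias is possible, not shown.

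A mean arm difference of 20 minutes would be extreme, since Table 3 gives 20 minutes as the maximal target for the whole interval from angiosuite arrival to puncture. At 5 minutes the shift is at most 0.030, or about 0.14 standard errors. The upper rows of the first table should be read in that light. The simulation confirms the algebra; it cannot show that a delay will occur in this trial.

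On section 9.2, puncture time is not named there, and on a plain reading a post-randomization interval is not baseline. But section 3.4 applies that very label to it, in similar terms, so one clarifying sentence is reasonable. Finally, section 9.0 refers to a separate SAP, which was not available for this review and may define the covariate differently.

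None of this answers the classification error itself, which holds whatever the delay turns out to be.

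**Conclusion.** The concern holds. Item 2c is labelled baseline but is measured after randomization, and the assigned treatment can affect it. The exploratory adjusted ORs may therefore miss part of the total effect of GA versus sedation. If GA delays puncture, the adjusted OR moves toward GA; if sedation does, it moves the other way.

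The size cannot be derived from the documents. Under the assumed ranges for GA delay, the adjusted OR is about 1% to 13% above the total-effect OR, and near the low end the distortion is negligible. The label error is certain on the documents' own definitions; the bias and its direction depend on the data. The correction should be made because it is free, not because the trial's main conclusion is at risk.

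**What to change.** 1. In section 3.4, replace item 2c with time from stroke onset (last seen normal) to randomization, as a continuous covariate. This keeps the prognostic adjustment and is finer than the two-level onset-time stratum already in the model.
2. Report onset-to-puncture and randomization-to-puncture times by arm as process outcomes. If the role of delay is of interest, use them only in an analysis labelled as mediation or direct effect.
3. Add to section 9.2 that puncture time does not count as a baseline variable for the imbalance-triggered analyses.
4. Check the separate SAP named in section 9.0 for the same covariate.

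The cost is one line in each of the two sections. No new data are needed: onset and randomization times are required for eligibility, stratification and web-based randomization, and section 6.2.1 already collects puncture timing.

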4.0 STUDY DESIGN

4.1 Overview

This trial is a multicenter, randomized, parallel-group, open-label treatment with blinded end point adjudication (PROBE). Patients with acute stroke who meet endovascular therapy criteria for large arterial vessel occlusion will be randomized 1:1 to Sedation or GA. Patients randomly assigned to GA will then be randomized to either inhalational or IV anesthesia using a 1:1 ratio.

The total estimated duration for trial completion is 2 years (18 months for enrollment, 6 months for data collection, data cleaning and statistical analysis); subject participation is expected for 90 days from onset of acute stroke event

4.2 Enrollment and Randomization

Enrollment in this study is defined as the moment when the randomization process is completed and the subject is assigned to a study arm. After randomization, no crossover is permitted unless either the neurovascular interventionalist or anesthesiologist determines the patient meets criteria as described in section 5.0. Randomization will occur via a secure, password-protected, web-based system. Subjects will be randomized 1:1 to GA or Sedation using permuted blocks and stratified by center, terminal ICA occlusion (yes/no), and time of stroke symptom onset (≤ 6 hours or 6-16 hours). Patients randomized to GA will subsequently be randomly assigned in a 1:1 ratio to either inhalational or IV anesthesia.

Stroke management and endovascular therapy procedures will occur as per local site usual care. Only FDA-approved thrombectomy devices should be used with first line use of stent retriever. Both general anesthesia and Sedation should be delivered and managed by an anesthesiologist.

5.0 STUDY POPULATION

5.1 Inclusion Criteria

1. Acute ischemic stroke due to large intracranial vessel occlusion demonstrated on CT-angiography in the following anterior circulation locations that will be treated by endovascular therapy (EVT):
 - a. Internal Carotid Artery (terminal “T” or “L-type”- occlusion)
 - b. Middle Cerebral Artery (MCA) M1 or proximal M2
 - c. Anterior Cerebral Artery (ACA) A1 or proximal A2
 - Patients who receive IV-tPA thrombolysis are eligible provided the drug was delivered within 4.5 hours of stroke onset or last seen normal and in accordance with local hospital standard of care.
 - Patients who receive TNKase are also eligible, given that drug was delivered in accordance with the local hospital standard of care.
2. Ages 18-90.
3. National Institute of Health Stroke Scale (NIHSS) score 6-30
4. Time of stroke symptom onset of last seen normal to start of EVT (defined as groin puncture) \leq 16 hours.
5. Limited infarct core, as defined below and adapted from the 2018 American Heart Association guidelines²⁸
 - a. For patients presenting \leq 6 hours from time of symptom onset or last seen normal, Alberta Stroke Program Early Computed Tomography Score (ASPECTS) \geq 6
 - b. For patients presenting $>$ 6 hours and \leq 16 hours from time of symptom onset or last seen normal, they must satisfy EITHER ONE of the two following criteria:
 - i. Ischemic core by CT Perfusion or MRI/MR Perfusion $<$ 70 mL, a ratio of volume of penumbral tissue to infarct core of \geq 1.8, and absolute volume of penumbral tissue of \geq 15 mL²⁹

OR

- ii. For patients with NIHSS \geq 10, infarct core of $<$ 31 mL by CT Perfusion or MRI; For patients with NIHSS \geq 20, infarct core $<$ 51 mL.³⁰
6. Subject willing/able to return for protocol required follow up visits.
7. No significant pre-stroke disability (modified Rankin Score must be \leq 2).
8. Females of childbearing potential must have a negative serum or urine pregnancy test.
9. Patient or patient’s legally authorized representative has given Informed Consent according to Good Clinical Practices (GCP) and/or local IRB policies.

